9.1.6.2. Secondary endpoints

- Change from baseline in catastrophising behaviour adopted by the patient (PCS-Pain Catastrophising Scale)^(34, 35)
- Change from baseline in coping adaptive strategy adopted by the patient (CSQ-Coping Strategies Questionnaire)⁽²⁹⁻³²⁾
- Percentage of patients with low disease activity (LDA) as assessed by DAS28-4 ESR/CRP < 3.2, SDAI ≤ 11, CDAI ≤ 10⁽³⁶⁾,
- Percentage of patients in remission as assessed by DAS28-4 ESR/CRP < 2.6, SDAI ≤ 3.3, CDAI ≤ 2.8, ACR-EULAR 2011 Boolean criteria (TJC ≤ 1 + SJC ≤ 1 + CRP ≤ 1 mg/dL + VAS patient ≤ 1)^(36, 37)
Change from baseline in score DAS28 ESR/CRP and in its components over time
- Evaluation of response to treatment considering outcome of the DAS28 (EULAR criteria)⁽³⁸⁾

Table 1: Evaluation of response to treatment considering outcome of DAS28 (EULAR criteria)

DAS28 at visit	Decrease in DAS28 compared to V0		
	>1.2	>0.6 and ≤1.2	≤0.6
≤3.2	Good responder	Moderate responder	Non-responder
>3.2 and ≤5.1	Moderate responder	Moderate responder	Non-responder
>5.1	Moderate responder	Non-responder	Non-responder

- Change from baseline in the number of painful joints (TJC) over time
- Change from baseline in the number of swollen joints (SJC) over time
- Evaluation of the possible existence of fibromyalgia (FIRST questionnaire)^(39, 40)
- Change from baseline in the duration of morning stiffness over time
- Change from baseline in patient compliance over time (GIRERD Questionnaire)⁽⁴¹⁾
- Change from baseline in overall health status over time (EuroQoL EQ-5D-3L questionnaire)⁽⁴²⁻⁴⁴⁾
- Change from baseline in quality of life over time (SF-12 questionnaire)⁽⁴⁵⁾
- Change from baseline in fatigue over time (FACIT-Fatigue questionnaire)^(46, 47)
- Evaluation of tolerability

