6.1.1.2.1 PCS – Pain Catastrophising Scale

The Pain Catastrophising Scale (PCS) is a 13 item questionnaire around thoughts and emotions experienced during pain, with each question on a 5 point scale (0 = 'Not at all' to 4 = 'All the time'). There are three subscales of PCS: Rumination (thinking deeply), exaggeration and helplessness. [Table 2](#) shows an overview of the items which belong to each domain.

Table 2 Overview of Domains for PCS ([5](#))

Domain	Items
Rumination	8, 9, 10, 11
Exaggeration	6, 7, 13
Helplessness	1, 2, 3, 4, 5, 12

Total scores and domain scores are derived by summing the scores of the individual items. The highest possible score of PCS is 52, and a total score of ≥ 20 indicates a clinically relevant level of catastrophisation. PCS will be considered both in terms of individual domain scores and total scores. PCS total score will be analysed as a continuous variable as well as a dichotomous variable (<20 vs ≥ 20).

For the handling of missing data when deriving PCS scores, see Section [7.4](#).

PCS is collected at all visits (Inclusion visit, V1, V2, V3, V4, V5, V6 and any additional visits in the case of discontinuation of Tofacitinib).

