6.1.1.2.2 CSQ – Coping Strategies Questionnaire

The Coping Strategies Questionnaire (CSQ) evaluates cognitive coping and, in its French version, is split into 5 domains: “Distraction”, “Catastrophising”, “Distancing from Pain”, “Ignoring Pain Sensations” and “Praying”. The CSQ consists of 21 items in total and for each item, subjects rate the frequency of their use of each coping strategy on a 4-point Likert-type scale. CSQ is collected on the CRF as the following: 1: Never, 2: Sometimes, 3: Often and 4: Very often. In order to consider values comparable to the standard CSQ French Version, the following mapping will be done.

CSQ Text Value	CRF Value	Map to standard value
Never	1	0
Sometimes	2	1
Often	3	2
Very Often	4	3

This endpoint is considered in terms of the 5 domains, and a total score is not considered for CSQ. Domain scores are derived by summing the individual items scores that make-up the domain. Details of the 5 domains are provided below.

Domain	Items as numbered on CRF	Domain Score Range
Distraction	2, 10, 11, 19, 20	0 – 15
Catastrophising	3, 9, 15, 18	0 -12
Distancing from Pain	1, 5, 13, 21	0 – 12
Ignoring Pain Sensations	6, 7, 8, 14, 16	0 – 15
Praying	4, 12, 17	0 - 9

CSQ is collected at all visits (Inclusion visit, V1, V2, V3, V4, V5, V6 and any additional visits in the case of discontinuation of Tofacitinib).

For the handling of missing CSQ data, see Section [7.5](#).

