8.2.6 Secondary Analyses

All secondary analyses will use the FAS. Secondary analyses will consider Tofacitinib Total as the treatment group. Summaries of secondary endpoints will be presented for Tofacitinib total, Tofacitinib as monotherapy and Tofacitinib as combination, using the treatment labels seen in Section 2.3.

Each endpoint will apply the specific rules for missing data as described in Section 7 but if there are missing data points after this, no missing data methods will be used to impute data for the secondary analyses.

All the analyses described hereafter in this section will be performed on all assessments collected before permanent Tofacitinib discontinuation (On-Treatment Analysis). In addition, analyses described in sub-sections 8.2.6.2, 8.2.6.3, 8.2.6.4 and 8.2.6.5 will be re-run on all available data including retrieved dropout data (Analysis on All Available Data).

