Further summaries will be produced to investigate the relationship between behavioural strategies and the adverse event (AE) groups Herpes Zoster and Serious Infections. Serious infections are as defined in Section 6.2. The summaries will be presented separately for the two groups, and are as follows:

- The baseline behavioural strategies (PCS total score, PCS (3 domains) and CSQ (5 domains)) statistics, summarized as per Section **Error! Reference source not found.**, will be presented for patients who experienced each AE of interest (Herpes Zoster/Serious Infection) and for patients who did not experience the AE of interest.
- The last behavioural strategies (PCS total score, PCS (3 domains) and CSQ (5 domains)) statistics, summarized as per Section **Error! Reference source not found.**, for measurements prior to the first occurrence of the AE of interest (for patients who experienced the AE of interest) will be presented. The last behavioural strategies measurements in the study for patients who did not experience the AE of interest will also be presented.
- Correlation between the number of AE's of interest and behavioural strategies (PCS total score, PCS (3 domains) and CSQ (5 domains)) at baseline will be

examined using the methods described in Section **Error! Reference source not found..**

- Correlation between the number of AE's of interest and the last behavioural strategies (PCS total score, PCS (3 domains) and CSQ (5 domains)) prior to the first occurrence of an AE will be examined using the methods described in Section **Error! Reference source not found..**
- The correlation between the adjusted number of AE's (see Section 6.2) and the adjusted AUC for PCS and CSQ (see Section **Error! Reference source not found..**) will be calculated and presented, as per Section **Error! Reference source not found..** This will be done for:
 - PCS total score.
 - The 3 domains of the PCS.
 - The 5 domains of the CSQ.
- The change in behavioural strategies (PCS total score, PCS (3 domains) and CSQ (5 domains)) before and after start of the first occurrence of the AE of interest will be presented for the subset of patients who experience the AE of interest, summarized as per Section **Error! Reference source not found..**

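### PCS and CSQ are read before the event in patients with Herpes Zoster or serious infection but at the last on-treatment value in the others, so a time trend in the scores can look like an association

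*SAP*

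**What the plan says.** SAP 8.2.6.1 opens the relevant block with its purpose: "Further summaries will be produced to investigate the relationship between behavioural strategies and the adverse event (AE) groups Herpes Zoster and Serious Infections". The bullets that follow differ in how they fix the time of the score.

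- The first bullet compares baseline PCS and CSQ in patients with and without the event. Both groups are read at the same time.
- The second bullet uses the last score. For patients with the event it is given "for measurements prior to the first occurrence of the AE of interest (for patients who experienced the AE of interest) will be presented". For the rest: "The last behavioural strategies measurements in the study for patients who did not experience the AE of interest will also be presented".
- A later bullet plans "Correlation between the number of AE's of interest and the last behavioural strategies" recorded before a first event. It does not say which score a patient with no event contributes.

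SAP 8.2.6 limits the data: "All the analyses described hereafter in this section will be performed on all assessments collected before permanent Tofacitinib discontinuation (On-Treatment Analysis". The additional run on all available data covers 8.2.6.2 to 8.2.6.5 and not 8.2.6.1.

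The scores are repeated measures: "PCS is collected at all visits (Inclusion visit, V1, V2, V3, V4, V5, V6" and "CSQ is collected at all visits (Inclusion visit, V1, V2, V3, V4, V5, V6", with an additional visit if tofacitinib is stopped between scheduled visits. Their movement over time is itself of interest, since Protocol 9.1.6.2 lists "Change from baseline in catastrophising behaviour adopted by the patient (PCS-Pain Catastrophising Scale" as a secondary endpoint and has a parallel item for CSQ.

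**The concern.** A patient with the event stops contributing at the event. A patient without it goes on contributing until treatment or follow-up ends. The second bullet therefore sets scores from earlier on drug beside scores from later on drug. If PCS falls on average during treatment, patients with the event show higher (worse) scores only because they were read sooner. If scores rise, the artefact runs the other way.

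Elsewhere the SAP does control timing. Figures 3 and 4 fix time points for the correlations and logistic models, 8.1.7 divides the area under the curve by time on study, and the first bullet here uses baseline. Only the last-value bullets lack such a rule.

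At stake is the reading of a table meant to show whether behaviour is related to two safety events of special interest. From the table alone, a reader could not separate a timing artefact from a signal.

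**Working it through.** **No planned figure to reproduce.** The documents give no figure for this comparison. Two inputs come from the sample-size calculation in Protocol 9.5, which reproduces: 50 × 0.3 = 15 variables, 15 × 10 = 150 discontinuations, 150 / 0.50 = 300 patients.

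**Inputs from the documents**
- Drug survival of 50% at 24 months and 300 patients (Protocol 9.5)
- Target visit days 1, 30, 91, 183, 365, 548 and 731 (SAP Table 9)
- On-treatment assessments only (SAP 8.2.6)

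**Assumptions, because the documents give no value**
- First event rate of 0.03 to 0.06 per patient-year, constant over time, on drug, and independent of the scores (no true association)
- Exponential time to discontinuation
- Mean PCS change of 3 to 8 points over 24 months, in one of three shapes: linear; exponential with a 6-month time constant; complete by Month 3

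**Method.** Patients were simulated under these inputs. Those with the event were read at the last scheduled visit before it. Those without were read (a) at the last scheduled visit on drug, or (b) at the end of time on drug, as when a discontinuation visit supplies the value. Both are shown because the SAP does not say whether a discontinuation visit counts as collected before discontinuation.

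**Number with the event.** The simulated proportion is 0.042 at the lower rate and 0.082 at the higher. 300 × 0.042 = 12.6 and 300 × 0.082 = 24.6, so about 13 to 25 patients per event type.

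**Mean reading day.** About 247 with the event; without it, about 482 under (a) and 518 under (b). The results barely move across the assumed rates.

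**False gap as a share of the 24-month change.** For a linear change the share is the difference in mean day over 730 days:
- (a) (482 − 247) / 730 = 0.32
- (b) (518 − 247) / 730 = 0.37

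The curved shapes come from the simulation. In points, the low end is the (a) share × 3 and the high end is the (b) share × 8.

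| Shape of change | Share, (a) | Share, (b) | PCS points for a change of 3 to 8 |
|---|---|---|---|
| Linear | 0.32 | 0.37 | 1.0 to 3.0 |
| 6-month time constant | 0.18 | 0.23 | 0.5 to 1.8 |
| Complete by Month 3 | 0.07 | 0.09 | 0.2 to 0.7 |

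With no mean change the gap is 0. If both groups are read at the same visit, the expected gap with no association is also 0.

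**Correlation bullet.** Two readings are open. If patients with no event are left out, the coefficient describes only patients with at least one event. If their last study value is used, the same timing difference enters the coefficient.

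**The case against.** The strongest reply is that this is a descriptive table. SAP section 4 states that there are no formal hypotheses, the bullet plans no test or estimated difference, and the baseline summary and baseline correlation already give a comparison at a common time. The documents also state no expected direction or size of change in PCS or CSQ. And with an assumed PCS standard deviation of 10 to 12 and 21 events, the standard error of a group difference is about 2.3 to 2.7 points, as large as most of the artefact.

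Much of this stands, and it is why the point is minor. It does not remove the problem. The timing difference shifts the expected contrast itself, and a table built to investigate a relationship will be read as a comparison whether or not a difference is printed.

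Three stronger readings are tempting, and the documents do not support them.

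- A reader might infer that patients without the event are all read at Month 24, which would widen the gap. SAP 8.2.6 restricts this section to on-treatment data, and under the 50% drug survival in Protocol 9.5 about half the patients would have no such value.
- A reader might infer that any improvement must show up as a material association. The size depends on when the change happens, and it is small if scores settle by Month 3.
- A reader might infer that the correlation bullet prescribes the same mismatch. It leaves the score for patients with no event undefined, which is a gap and not a stated rule.

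**Conclusion.** The last-value bullet is wrong as written, with minor consequences. It reads the two groups at different times on drug, by a mean of about 235 to 271 days under the stated assumptions (482 − 247 and 518 − 247). The resulting false gap is about 0.2 to 3.0 PCS points for an assumed 24-month change of 3 to 8 points. Patients with the event look worse if scores improve and better if scores worsen. The shares apply equally to any PCS domain or CSQ domain with the same shape of change.

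The asymmetry is in the text and needs no assumption. The size rests on an assumed event rate, an assumed size and shape of change, and the protocol's planning value for drug survival. The correlation bullet needs a definition before it can be programmed.

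**What to change.** Keep the baseline comparison. Replace the last-value contrast with a visit-matched table: at each scheduled visit, among patients on treatment and still free of the event, summarise PCS and CSQ by whether the first event of interest occurs before the next visit.

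For the correlation bullet, either apply the same aligned timing or state that it is restricted to patients with at least one event.

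A Cox model for time to first event, with the most recent PCS or CSQ score as a time-dependent covariate, could be added as exploratory. It should not be the main remedy with about 13 to 25 events per type.

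The cost is SAP wording and slightly more programming on data already collected. The downside is sparse cells: 13 to 25 events over six between-visit intervals average about 2 to 4 per interval. If one summary is wanted, average the visit-specific differences weighted by the number of events. Pooling all visits without regard to visit would bring timing back in.

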8.1.2 Correlation Analysis

The correlation between behavioural strategies (measured by PCS total score and 5 domains of the CSQ) and effectiveness will be studied with Pearson's or Spearman's coefficient according to the nature of variables compared. This will be calculated for all effectiveness endpoints. To investigate the relationship between a categorical variable and a continuous variable, boxplots for each category will be produced and a visual comparison will be made (there will be no correlation co-efficient for these comparisons).

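### The correlation of AE count with the last PCS/CSQ score before the first AE is, read literally, confined to patients with the event, and its baseline companion ignores time at risk

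*SAP*

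**What the plan says.** The last part of SAP 8.2.6.1 lists six summaries relating PCS (total and three domains) and CSQ (five domains) to Herpes Zoster and, separately, to serious infections. Two are at issue.

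- Third item: "Correlation between the number of AE's of interest and behavioural strategies", with the scores taken at baseline.
- Fourth item: "Correlation between the number of AE's of interest and the last behavioural strategies", with the score taken "prior to the first occurrence of an AE will be examined".

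I take the method to be that of SAP 8.1.2, where correlations are "studied with Pearson's or Spearman's coefficient". Neither item mentions time at risk.

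Three neighbouring items matter.

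- First item: baseline scores "will be presented for patients who experienced each AE of interest (Herpes Zoster/Serious Infection) and for patients who did not experience the AE of interest".
- Second item: the last score before the first event of interest in patients who had it, with this rule for the others: "The last behavioural strategies measurements in the study for patients who did not experience the AE of interest will also be presented".
- Fifth item: "The correlation between the adjusted number of AE's (see Section 6.2) and the adjusted AUC for PCS and CSQ". The adjusted number is the count divided by time on study (SAP 6.2). The AUC runs from baseline to the last follow-up visit (SAP 8.1.7).

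SAP 8.2.6 assigns these analyses to the FAS and limits them to assessments made before permanent discontinuation. SAP Section 4 states that the study has no formal hypotheses.

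**The concern.** The natural question is whether catastrophising or coping is associated with later zoster or serious infection, the two events SAP 6.2 singles out. A patient with no event has no score before a first event, and the fourth item gives no substitute. It would then correlate the score with a count that is almost constant. If every count is 1, neither Pearson nor Spearman exists; otherwise a few patients with repeat events determine it.

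The third item keeps patients with a count of zero but treats a patient observed briefly like one observed for 24 months. If behaviour also changes how long a patient is at risk, the coefficient mixes the two effects. The SAP's first secondary objective asks whether behaviour affects time on drug.

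**Working it through.** **The plan's own figure.** Protocol 9.5: k = 50 × 0.3 = 15 variables; 10 × 15 = 150 events; 150 / 0.50 = 300 patients. This reproduces. SAP 2.1 still says 500; I use 300. The documents give no rate or sample size for the AE correlations.

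**Inputs.** From the documents: 300 patients, 50% drug survival at 24 months, follow-up planned for 24 months whether or not tofacitinib continues (SAP 2.2). Assumed: exponential time on drug, Poisson counts, and event rates r of 1 to 10 per 100 patient-years.

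**Time at risk on treatment.** Hazard = ln 2 / 2 = 0.3466 per year. Mean time within 24 months = (1 − 0.5) / 0.3466 = 1.44 years. Total = 300 × 1.4427 = 433 patient-years.

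**Fourth item, read literally.** For time t, P(0) = exp(−rt) and P(1) = rt·exp(−rt), averaged over t when counting is on-treatment. Then:

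- cases = 300 × (1 − P(0));
- share with exactly one event = P(1) / (1 − P(0));
- chance that every case has a count of 1, so no coefficient exists = (1 − P(≥2))^300.

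Example with the full 24 months at 4 per 100: rt = 0.08, P(0) = 0.9231, P(1) = 0.0738, P(≥2) = 0.00303. The share is 0.0738 / 0.0769 = 96%, and 0.99697^300 = 0.40.

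| Rate per 100 PY | Cases, on-treatment | Exactly one event | No coefficient | Exactly one event, full 24 months | No coefficient, full 24 months |
|---|---|---|---|---|---|
| 1 | 4.3 | 99.1% | 96% | 99.0% | 94% |
| 2 | 8.5 | 98.2% | 86% | 98.0% | 79% |
| 4 | 16.7 | 96.5% | 56% | 96.1% | 40% |
| 6 | 24.6 | 94.8% | 28% | 94.1% | 14% |
| 10 | 39.7 | 91.5% | 3% | 90.3% | <1% |

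Simulation that also counted fewer than three cases as not computable gave 97%, 86%, 58%, 28% and 4% on-treatment. Repeat events in susceptible patients soften this only partly. At 4 per 100 with gamma frailty, about 90% of cases still have one event at variance 2, and no patient has a second event in 34% of studies at variance 1. Where the coefficient exists it carries little: with a true rate ratio of 1.5 per SD it reached p<0.05 in 0 to 7% of runs.

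**Fourth item with the second item's rule carried over.** Zero-count patients return, but cases are scored before their event and the others at their last measurement. With no true effect and scores falling 0.5 SD over the first year, false positives were 6 to 9%. The wording adds a further doubt: the item says an AE, not the AE of interest. If any AE is the anchor, some zero-count patients enter, scored before an unrelated event, and patients with no AE at all still have no score.

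**Third item.** Simulated with Spearman on raw counts against Poisson regression with a log-time offset, 1,000 runs per setting. With on-treatment counting and no true effect, false positives were:

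| Rate per 100 PY | HR 1.5 per SD: raw / offset | HR 2.0 per SD: raw / offset |
|---|---|---|
| 2 | 6.6% / 5.1% | 9.4% / 4.9% |
| 4 | 7.9% / 5.7% | 13.2% / 5.8% |
| 6 | 9.2% / 4.2% | 16.2% / 5.5% |
| 10 | 11.4% / 4.2% | 23.9% / 5.2% |

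HR is the hazard ratio for discontinuation. The Monte Carlo standard error near 5% is √(0.05 × 0.95 / 1,000) = 0.7 points. The raw-count errors were almost all in the negative direction. With a true rate ratio of 1.5 and a discontinuation HR of 1.5, power at 2, 4 and 6 per 100 was 13%, 15% and 24% raw against 24%, 37% and 52% with the offset. With equal 24-month follow-up, the raw count does as well as the rate: 4 to 5% false positives, and power of 29%, 49% and 67%.

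**Do the other items fill the gap?** The first and second contrast patients with and without the event, but without time at risk. The fifth adjusts for time, but its AUC includes scores after the event. Dividing the count by time and keeping Spearman barely helps: 12.5% false positives against 13.1% for the raw count at 4 per 100 and HR 2.0.

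**The case against.** The best defence is that the fourth item never says zero-count patients are dropped. The second item defines a last score for them, and the sponsor may have meant it to apply. That stands as a point about intent: the event-only reading is the literal one, not the only one. It does not save the analysis, since the carried-over rule compares scores taken at non-comparable times.

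The defence of the third item is stronger. A reader might infer that neither correlation can show anything, or that the baseline one will hide a real association. The documents do not support that. It includes all patients, and its bias needs two conditions. AE counting must be tied to time on drug, yet SAP 8.2.6 restricts assessments without stating an AE counting window, and SAP 6.2 uses time on study. Behaviour must also affect time at risk, which the study investigates but does not assume; Protocol Section 7 says no such data exist. With milder effects the gain is small: at 4 per 100 with a rate ratio and a discontinuation HR both of 1.3, power is 11% raw and 18% with the offset, and raw-count false positives at HR 1.3 are only 5.4%.

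Nor does the SAP lack every event/no-event contrast or time adjustment; the first, second and fifth items provide them in part. Finally, these summaries are descriptive, no decision hangs on them, and SAP 8.1.2 promises coefficients without mentioning p-values. That limits the priority.

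**Conclusion.** The point holds in two parts of unequal strength. Read literally, the fourth item gives a coefficient that is often not computable and cannot distinguish patients who get zoster or serious infection from those who do not. This rests on assumed event rates, but the share of cases with a single event stays at about 90% or more throughout the range examined. The alternative reading is computable but distorted if scores drift over time. The third item is valid if time at risk is equal or unrelated to the score, and biased if behaviour affects it; the 7 to 24% false-positive range applies only to on-treatment counting with a discontinuation HR of 1.5 to 2.0 per SD. No other item in the list supplies a comparison that uses both time at risk and a score known to precede the event. Priority is low to moderate.

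**What to change.** - Delete the fourth-item correlation.
- Replace the third with a Poisson or negative binomial regression of the number of events of interest on the baseline score, in the FAS. State the AE counting window and use the log of that time as offset: time on study, or time on tofacitinib plus the SAP's 28-day lag if counts are treatment-emergent. Report the rate ratio per SD with its 95% confidence interval.
- If the latest score before the event is wanted, use a Cox model for time to the first event of interest with the score as a time-dependent covariate, so that patients without the event contribute.

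The cost is SAP wording and 9 scores × 2 event types = 18 simple models in place of 36 correlations, with no new data. The downside is wide intervals. Even with the offset, power in the simulations was only 24 to 52% at 2 to 6 per 100 patient-years for a rate ratio of 1.5 per SD, so the estimates should be presented as exploratory.
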